12.4.5 Subgroup Analysis

Subgroup analyses of the primary and key secondary endpoints will be performed a priori for the following pair of subgroups:

- FPG ≥180 at baseline
- FPG < 180 at baseline

The study is not formally powered to detect statistical significance within or among subgroups, and hence any hypothesis testing comparing results within or between these cohorts will be considered in that context. Observance of trends and qualitative comparisons between the subgroups will therefore be of greatest interest.

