7.13.1 Screening Visit – Visit 1 (within 84 days from the Index Procedure)

To limit in-person visit, the screening visit may be performed remotely. Screening BMI eligibility will be based on self-reported height and weight. Potentially eligible participants will be scheduled for laboratory tests at the study laboratory. The following procedures/assessments will be performed during this visit:

- Informed consent prior to the conduct of any study-related procedures
- Inclusion and exclusion criteria
- Demographics
- Medical history including diseases, disorders and medications
- Diabetes history including diabetes medications
- Laboratory tests:
 - o Hematology (CBC with differentials)
 - Metabolic panel (liver and renal function)
 - o Fasting serum C-peptide, FPG, HbA1C

- GAD antibodies
- o TSH
- H. Pylori (breath or stool test)
- Pregnancy test for females capable of becoming pregnant
- Registration on screening log

Once all data including testing results related to the screening have been obtained, the investigator will review the participant's eligibility for the study. If deemed eligible, participant will be scheduled for the baseline visit.

Eligible participant must meet all the inclusion criteria and none of the exclusion criteria with one exception. If a participant has met all other criteria except that s/he has been on stable glucose-lowering medication(s) for less than 12 weeks at the time of screening visit, the participant can be scheduled for baseline visit such that s/he will be on stable medication for 12 weeks at the time of baseline visit.

It is recognized that COVID-19 restrictions may cause delays in scheduling the index procedure, resulting in the screening visit being out of window. In case the screening visit is out of the visit window, the investigator will reassess the participant's eligibility by evaluating any changes in the participant's medical history and medications. The investigator may decide to repeat certain screening tests based on his/her medical judgement. If the investigator determines that the participant remains eligible for participating in the study, the participant may proceed to Baseline visit. Investigator's assessment and any repeated test results will be documented on eCRFs.

7.13.2 Baseline Visit – Visit 2 (within 21 days prior to the Index Procedure)

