12.4.4 Effectiveness Analysis

Secondary endpoints are summarized in Section 3. The primary analysis of the study's secondary endpoints will be performed using the mITT population. The analysis will also be performed using the PP population when appropriate.

Results for these endpoints will be tabulated and reported for each treatment arm at each timepoint for which data were specified to be collected, using change scores from baseline where appropriate. For binary outcomes, Fisher's exact test will be used to assess differences which may be present between groups, while t-tests or Wilcoxon's rank-sum will be applied for continuous outcomes depending on the normality assumption. Effectiveness endpoints collected at multiple timepoints post-intervention (e.g., HbA1c) will also be assessed longitudinally using repeated-measures mixed-effects models with time as the repeated measure and treatment arm as a factor variable. Assessment of overall change from baseline and comparisons between treatment arms will then be predicated principally upon these repeated-measures analyses.

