### 4.2.1. Secondary Endpoints

**First Secondary Endpoint:** Procedure success: defined as successful treatment of at least 6 cm of duodenum segment.

**Second Secondary Endpoint:** Procedure time: defined as the time between the Endogenex catheter insertion and the catheter removal.

Third Secondary Endpoint: Change from baseline (post-baseline minus baseline) in HbA1c reported for each pre-specified study visit.

Note: The estimates will be derived using a mixed model repeated measure procedure; the 24 week result will be the principal time point of interest.

**Fourth Secondary Endpoint:** Change from baseline (post-baseline minus baseline) in Fasting plasma glucose (FPG) reported for each pre-specified study visit.

Note: The estimates will be derived using a mixed model repeated measure procedure; the 24 week result will be the principal time point of interest.

**Fifth Secondary Endpoint:** Change from baseline (post-baseline minus baseline) in Insulinresistance by HOMA-IR reported for each pre-specified study visit.

Note: The estimates will be derived using a mixed model repeated measure procedure; the 24 week result will be the principal time point of interest.

**Sixth Secondary Endpoint Part 6a:** Change from baseline (post-baseline minus baseline) in Post-prandial plasma glucose (PPG) based on mixed meal tolerance test (MMTT) reported for each prespecified study visit.

Note: The estimates will be derived using a mixed model repeated measure procedure; the 12 week result will be the principal time point of interest.

**Sixth Secondary Endpoint Part 6b:** Change from baseline (post-baseline minus baseline) in beta cell function based on mixed meal tolerance test (MMTT) reported for each pre-specified study visit.

Note: The estimates will be derived using a mixed model repeated measure procedure; the 12 week result will be the principal time point of interest.

**Sixth Secondary Endpoint Part 6c:** Change from baseline (post-baseline minus baseline) in the disposition index based on mixed meal tolerance test (MMTT) reported for each pre-specified study visit.

Note: The estimates will be derived using a mixed model repeated measure procedure; the 12 week result will be the principal time point of interest.

**Seventh Secondary Endpoint:** o Time in range, glucose variability by continuous glucose monitoring (CGM)

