All mean and median values will be formatted to one more decimal place than the measured value. Standard deviation values will be formatted to two more decimal places than the measured value. Minimum and maximum values will be presented with the same number of decimal places as the measured value.

The number and percentage of responses will be presented in the form XX (XX.X%).

Version 1.0 Confidential Page 19 of 42

- All summary tables will include the analysis population sample size (i.e., number of patients).
- Relative Study Day 1 is defined as the day the patient underwent the DMR study procedure. All study days are determined relative to the day the patient underwent the DMR study procedure.
- Baseline values will be defined as those values recorded immediately prior to the DMR study procedure.
- Change from baseline for ratio data will be calculated as follows:

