# 7.3.2. Subgroup Analyses: Assessing the Effect of Pre-Specified Factors on a Continuous Parameter

Based on the limited enrollment and sample size from the clinical investigation, the proposed tabulations for the individual subgroups may not be possible. Subgroup analyses will follow the follow approach where possible and if it is clinically indicated to address a specific research question.

The breakdown of safety and effectiveness will follow the FDA Guidance entitled *Evaluation and Reporting of Age-, Race-, and Ethnicity-Specific Data in Medical Device Clinical Studies* (Document issued on September 12, 2017). Specifically, the guidance provided in Section VI. entitled *Recommendations for Submitting Age-, Race-, and Ethnicity-Specific Data in Submissions to the Agency and Reporting in Public Documents*, Part A: Enrollment Demographics, Baseline Characteristics & Co-Morbidities.

Subgroup analyses by the following baseline characteristics will be provided if there are a sufficient number of patients that warrant this breakdown:

- age group ( $<65, \ge 65$  years)
- race
- sex
- ethnicity
- duration of diabetes (<median, ≥median)
- duration of diabetes ( $\leq 5$ ,  $\geq 5$  to  $\leq 10$ ,  $\geq 10$  years)
- HbA1c ( $\leq 8.5\%$ , > 8.5%)
- renal impairment (eGFR <60,  $\ge$ 60 mL/min/1.73m2), and
- BMI group ( $<30, \ge 30 \text{ to } <35, \ge 35 \text{ kg/m2}$ ).

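### Splitting on baseline FPG and then comparing change from that same FPG builds in a larger apparent fall in the high-FPG subgroup

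*Protocol*

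**What the plan says.** Protocol 12.4.5 states that "Subgroup analyses of the primary and key secondary endpoints will be performed a priori" for a single pair: "FPG ≥180 at baseline" and FPG below 180 at baseline. No unit is given; I take mg/dL. The section concedes that the study is not powered for subgroups and concludes: "Observance of trends and qualitative comparisons between the subgroups will therefore be of greatest interest". It does not name the key secondary endpoints.

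Protocol 12.4.4 analyses secondary endpoints "using change scores from baseline where appropriate". SAP 4.2.1 defines the FPG endpoint as "Change from baseline (post-baseline minus baseline) in Fasting plasma glucose (FPG) reported for each pre-specified study visit", and SAP 7 fixes the subtracted value: "Baseline values will be defined as those values recorded immediately prior to the DMR study procedure". The mixed model in Protocol 12.4.4 names time and treatment arm but no baseline covariate. Protocol 4.1 describes a treatment-only study. Neither document mentions regression to the mean.

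The SAP's own subgroup list (7.3.2) is conditional: "Subgroup analyses by the following baseline characteristics will be provided if there are a sufficient number of patients that warrant this breakdown". It includes HbA1c split at 8.5% and omits the FPG split.

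A second fasting reading usually exists. The screening laboratory tests in Protocol 7.13.1 include "Fasting serum C-peptide, FPG, HbA1C", and the Schedule of Activities repeats FPG and HbA1c at baseline. Protocol 7.13.2 allows the two visits to be combined, and one set of data then serves as both.

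**The concern.** A single FPG reading is the person's usual level plus short-term variation. Participants at or above 180 include some placed there by a high reading, and those below include some placed there by a low one. At follow-up the first group drifts down and the second drifts up with no device effect. Because the same reading is the baseline of the change score, the drift enters the subgroup comparison in full, always in the direction that favours the high-FPG group.

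This is bias, not imprecision, so the caveat about power does not cover it. A qualitative reading of trends is also the reading most exposed to a trend that the method creates. At stake is a mistaken conclusion that participants with higher fasting glucose gain more glucose lowering from the procedure.

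**Working it through.** The plan gives no SD, correlation or subgroup figure to reproduce, so the size below rests on stated assumptions.

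**Inputs from the documents:** cut at 180; change = follow-up minus the last pre-procedure value; 20 participants; no untreated arm; HbA1c entry limits 7.5% to 10% (inclusion criterion 4 and exclusion criterion 41).

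**Assumed:** no treatment effect and no time trend; normal readings with independent errors; population mean FPG 180 mg/dL; between-person SD 40; within-person SD 15, 20 or 25.

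**FPG change, split on the baseline reading.** Let ρ be the share of total variance that lies between persons. With the cut at the mean, the gap in mean change (high minus low) is

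-(1 - ρ) × 2 × √(2/π) × SD_total, where 2 × √(2/π) = 1.596.

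| Within-person SD | SD_total | 1 - ρ | Gap (mg/dL) |
|---|---|---|---|
| 15 | √(1600 + 225) = 42.7 | 225/1825 = 0.123 | -8.4 |
| 20 | √(1600 + 400) = 44.7 | 400/2000 = 0.200 | -14.3 |
| 25 | √(1600 + 625) = 47.2 | 625/2225 = 0.281 | -21.1 |

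Simulation agrees. With within-person SD 20 and 20 participants, the high group appears to fall more in about 87% of trials with no effect.

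**Wider assumptions.** With mean 165 to 195, total SD 30 to 50 and ρ from 0.5 to 0.95, the gap runs from -2.4 to -40.4 mg/dL and never changes sign. At mean 180 and total SD 40:

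| ρ | Gap (mg/dL) | High group looks better | Nominal 5% t-test rejects |
|---|---|---|---|
| 0.5 | -31.9 | 97% | 43% |
| 0.7 | -19.2 | 92% | 27% |
| 0.85 | -9.6 | 84% | 15% |
| 0.95 | -3.2 | 71% | 8% |

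**FPG change, split on the screening reading.** If screening and baseline errors are independent, the gap is about 0, the high group looks better in about 50% of trials, and the t-test rejects in about 5%. If those errors have correlation c, the gap is c times the baseline-split gap. For within-person SD 20 this is 0.3 × -14.3 = -4.3 and 0.5 × -14.3 = -7.1 mg/dL.

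**HbA1c change, split on FPG.** Assumed: HbA1c mean 8.6, SD 1.0, reliability 0.8 to 0.9; FPG reliability 0.7; correlation of true levels 0.7. With independent errors the gap is 0.00 before the entry limits and +0.06 to +0.10 points within them, favouring the low-FPG group. If short-term errors in FPG and HbA1c have correlation 0.3 to 0.6, the gap within the limits is -0.01 to -0.13. The sign is not predictable.

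**HbA1c change, split on baseline HbA1c at 8.5% (SAP 7.3.2).** Assumed: between-person SD 1.0, error SD 0.3, entry limits applied at both visits. The gap is about -0.14 points split by baseline value and about +0.06 split by screening value. The reversal arises because the entry limits also truncate the baseline reading.

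**The case against.** The best case against the point is that little depends on these subgroups. The study is a feasibility study, Protocol 3 calls the efficacy assessment exploratory, SAP 7.1 says testing is for information only, and the SAP may produce no subgroup tables at all with 20 participants. That limits the weight of any subgroup result. It does not remove a one-directional bias from the protocol's only a priori pair.

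A reader might infer more than the documents support:

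- **That every subgroup comparison is biased.** The primary endpoint is a proportion with a device- or procedure-related serious adverse event and has no change score.
- **That the high-FPG group will look like better responders.** The only responder definitions are HbA1c falls of at least 0.5 points. They subtract HbA1c, not FPG, and the bias that reaches them can take either sign.
- **That FPG change is certain to be subgrouped.** The key secondary endpoints are unnamed, so this is likely but not confirmed.
- **That the stated interest in trends extends to the SAP's HbA1c split.** That sentence in Protocol 12.4.5 concerns only the FPG pair, and the SAP split is conditional.
- **That the result will choose patients for a later study.** Neither document says so.

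The size is also open to challenge, since the SDs and correlations are assumed. The direction does not depend on them.

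**Conclusion.** The point holds in a limited form. For FPG change, and for HOMA-IR so far as it uses the same fasting glucose (the documents give no formula), the split in Protocol 12.4.5 creates a spurious advantage for the high-FPG group and nothing in the plan corrects it. The size is about -8 to -21 mg/dL for within-person SD 15 to 25 with mean 180 and between-person SD 40, and about -2 to -40 over wider assumptions. The SAP's HbA1c split at 8.5% has the same fault for HbA1c change, about -0.14 points under the assumed SDs, if that analysis is run. The primary endpoint is not affected, and HbA1c change under the FPG split has no predictable bias.

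**What to change.** 1. In Protocol 12.4.5, for FPG change and HOMA-IR, assign the subgroup from the separate screening-visit FPG and keep the baseline-visit value for the change score. Name the key secondary endpoints and state the unit of the cut.
2. Where screening and baseline were one visit, leave the participant out of this comparison, or show the baseline-classed result only with a stated regression-to-the-mean caveat. Do not substitute mean CGM glucose: 180 is not an equivalent cut on that scale, and CGM time in range is itself an endpoint whose baseline would come from the same data.
3. For the HbA1c split in SAP 7.3.2, show results by screening and by baseline value with the same caveat. Reclassing alone leaves a smaller gap in the opposite direction.
4. Reconcile the two subgroup lists, since the SAP omits the protocol's FPG pair.

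No new data are needed, but there are costs. Screening FPG may be up to 12 weeks old, and Protocol 7.13.1 lets screening precede 12 weeks of stable medication. Some bias remains if screening and baseline errors are correlated. Combined-visit participants leave an already small comparison. SAP 3 already tabulates all 20 patients, so the change redefines a subgroup after enrolment in an open-label study and should be recorded as such.

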13 QUALITY CONTROL AND QUALITY ASSURANCE

13.1 Selection of Study Sites and Investigators

The sponsor will select investigators who are qualified by training and experience to perform clinical research in this field and to participate in the clinical investigation. Sites will be selected based upon an assessment of the qualifications of the Primary Investigator and the facilities at each site. All investigators will be trained on the device, the protocol and all study procedures prior to enrolling participants.

A pre-investigation visit will be conducted at each study site to assure that the investigator and the study staff understand the obligations for using and managing the investigational device, following the study protocol, obtaining informed consent, adhering to GCP and FDA regulations, and conducting clinical research.

13.2 Training

13.2.1 Site Training

All investigators/study personnel are required to attend sponsor training sessions, which may be conducted at a site initiation visit or other appropriate training sessions. Remote over-the-phone or web-based training will take place as necessary. Training of investigators/study personnel will include, but is not limited to, the investigational plan, participant recruitment, enrollment (including review of inclusion and exclusion criteria), participant retention, investigational device usage, protocol requirements, case report form completion, and study personnel responsibilities. All investigators/study personnel that are trained must sign a training log (or an equivalent) upon completion of the training. Investigator/study personnel must not perform any study-related procedures prior to being trained.

Investigators who perform the Endogenex procedure will be trained on device use. Sponsor personnel will provide technical support for all the Endogenex procedures during the study.

13.2.2 Monitor Training

The sponsor or designee will engage monitors that are qualified by appropriate training and experience to review the conduct and quality of the study. Prior to working on the study, monitors will be trained to the investigational plan, case report forms, and the device/procedure knowledge. Such training will be documented.

13.3 Study Monitoring

Sponsor and/or a designee (e.g., a Contract Research Organization), will monitor the clinical study in a manner consistent with FDA regulations and the Good Clinical Practice (GCP) standards adopted by the sponsor.

The investigator is required to ensure compliance with all procedures required by the Investigational plan and by study procedures provided by the sponsor. The investigator agrees to provide reliable data and all information requested by the Investigational Plan including eCRFs, discrepancy clarification requests or other appropriate instruments according to the instructions provided, and to ensure direct access to source documents by sponsor representatives.

Study monitoring provides the sponsor with the opportunity to evaluate the progress of the study, to verify the accuracy and completeness of eCRFs, to resolve any inconsistencies in the study records, and to ensure that all protocol requirements, applicable regulatory requirements, and investigator's obligations are being fulfilled. Centralized data review will be performed to identify missing data, data inconsistencies, potential protocol deviations, unusual trends, site performance, etc. Source data verification (SDV) will be performed remotely and/or onsite to ensure data accuracy. Periodical onsite monitoring visit will be performed to ensure study compliance, adequate adverse event reporting, and to perform other tasks that can't be accomplished remotely.

The investigator and his/her staff will be expected to cooperate with sponsor's personnel or designee and to be available during the monitoring visits to answer questions sufficiently and to provide any missing information. Monitoring visits may be performed remotely, especially in consideration of COVID-19. The Investigator and his/her staff will provide necessary assistance to facilitate remote monitoring.

13.4 Source Data Verification

Source data verification ensures accuracy and credibility of the data obtained. During monitoring, reported data is reviewed with regard to being accurate, complete, and verifiable from source documents (e.g., participant files, physician notes, discharge summaries, operative records, study worksheets, etc.). All data reported on the eCRF should be supported by source documents, unless the eCRF also serves as a source document. Source data verification may be performed remotely.

13.4.1 Definition of Source Data

Source data includes all information in source documents (original records, certified copies of original records, appointment books, original laboratory records, CGM data, and original data recorded on customized worksheets) and includes all original recordings or copies of clinical findings, observations, or other activities in a clinical study necessary for the reconstruction and evaluation of the study. Certain data may be directly entered into eCRF. In this case, the eCRF serves as source document.

13.4.2 Direct Access to Source Data/Documents

The investigator(s)/institution(s) will permit direct access to source data/documents for study-related monitoring, audits, IRB and regulatory inspection(s). For remote source data verification, the Investigator and his/her staff will provide the study monitor remote access to source records.

Consenting participants are agreeing to allow the sponsor or designee access and copying rights to pertinent information in their medical records and their CGM data relevant to study participation. As part of the informed consent, the investigator or designee will obtain permission for regulatory authorities to review any records identifying participants in this study. The sponsor will not otherwise release any personal information (refer to **Section 15.3** Confidentiality).

13.5 Protocol Deviations

It is the investigator's responsibility to ensure that there are no deviations from the protocol except in cases of medical emergencies, when the deviation is necessary to protect the life or physical well-being of the participant. In the event of any deviation from the protocol, a Protocol Deviation Form will be completed. The occurrence of protocol deviations will be monitored by the sponsor for evaluation of investigator compliance to the protocol, Good Clinical Practice (GCP), and regulatory requirements. The investigator will inform the IRB of protocol deviations according to requirements of each reviewing IRB.

A protocol deviation for this protocol consists of, but is not limited to, the following:

- Failure to obtain participant's informed consent prior to any study-specific activities and the index procedure
- Enrollment of participants who do not meet all eligibility requirements
- Failure to conduct protocol required clinical follow-ups and within time windows
- Failure to report SAEs according to protocol requirements

In the event of any deviation from the protocol, the investigator will be notified of the site's non-compliance. Corrective actions will be advised if necessary and the methods, plan or other activities put in place to ensure non-recurrence will be documented by the investigator and forwarded to the sponsor or their designee. Continued protocol deviations despite re-education of study site personnel and/or persistent protocol deviations may result in termination of the site's study participation. Participants already enrolled at these sites will continue to be followed per protocol guidelines.

